8.3.1.1. Reporting SAEs to Pfizer Safety

All SAEs occurring in a participant during the active collection period as described in [Section 8.3.1](#) are reported to Pfizer Safety on the CT SAE Report Form immediately upon awareness and under no circumstance should this exceed 24 hours, as indicated in [Appendix 3](#). The investigator will submit any updated SAE data to the sponsor within 24 hours of it being available.

8.3.1.2. Recording Nonserious AEs and SAEs on the CRF

All nonserious AEs and SAEs occurring in a participant during the active collection period, which begins after obtaining informed consent as described in [Section 8.3.1](#), will be recorded on the AE section of the CRF.

The investigator is to record on the CRF all directly observed and all spontaneously reported AEs and SAEs reported by the participant.

Reporting of AEs and SAEs for participants who fail screening are subject to the CRF requirements as described in [Section 5.4](#).

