8. STUDY ASSESSMENTS AND PROCEDURES

The investigator (or an appropriate delegate at the investigator site) must obtain a signed and dated ICD before performing any study specific procedures.

Study procedures and their timing are summarized in the [SoA](#). Protocol waivers or exemptions are not allowed.

Safety issues should be discussed with the sponsor immediately upon occurrence or awareness to determine whether the participant should continue or discontinue study intervention.

Adherence to the study design requirements, including those specified in the [SoA](#), is essential and required for study conduct.

All screening evaluations must be completed and reviewed to confirm that potential participants meet all eligibility criteria. The investigator will maintain a screening log to record details of all participants screened and to confirm eligibility or record reasons for screening failure, as applicable.

Participants will be screened within 28 days prior to administration of the study intervention to confirm that they meet the study population criteria for the study. If the time between screening and dosing exceeds 28 days as a result of unexpected delays (eg, delayed drug shipment), then participants do not require rescreening if the laboratory results obtained prior to first dose administration meet eligibility criteria.

A participant who qualified for this protocol but did not enroll from an earlier cohort/group may be used in a subsequent cohort/group without rescreening, provided laboratory results obtained prior to the first dose administration meet eligibility criteria for this study. In addition, other clinical assessments or specimen collections, eg, banked biospecimens, may be used without repeat collection, as appropriate.

Every effort should be made to ensure that protocol required tests and procedures are completed as described. However, it is anticipated that from time to time there may be circumstances outside the control of the investigator that may make it unfeasible to perform the test. In these cases, the investigator must take all steps necessary to ensure the safety and well-being of the participant. When a protocol required test cannot be performed, the investigator will document the reason for the missed test and any corrective and preventive actions that he or she has taken to ensure that required processes are adhered to as soon as possible. The study team must be informed of these incidents in a timely manner.

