8.3.1. Time Period and Frequency for Collecting AE and SAE Information

The time period for actively eliciting and collecting AEs and SAEs (“active collection period”) for each participant begins from the time the participant provides informed consent, which is obtained before the participant’s participation in the study (ie, before undergoing any study related procedure and/or receiving study intervention), through and including a minimum of 28 calendar days, except as indicated below, after the last administration of the study intervention.

Follow-up by the investigator continues throughout and after the active collection period and until the AE or SAE or its sequelae resolve or stabilize at a level acceptable to the investigator.

For participants who are screen failures, the active collection period ends when screen failure status is determined.

If the participant withdraws from the study and also withdraws consent for the collection of future information, the active collection period ends when consent is withdrawn.

If a participant permanently discontinues or temporarily discontinues study because of an AE or SAE, the AE or SAE must be recorded on the CRF and the SAE reported using the CT SAE Report Form.

Investigators are not obligated to actively seek information on AEs or SAEs after the participant has concluded study participation. However, if the investigator learns of any SAE, including a death, at any time after a participant has completed the study, and he/she considers the event to be reasonably related to the study intervention, the investigator must promptly report the SAE to Pfizer using the CT SAE Report Form.

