8.3.3. Follow-up of AEs and SAEs

After the initial AE or SAE report, the investigator is required to proactively follow each participant at subsequent visits/contacts. For each event, the investigator must pursue and obtain adequate information until resolution, stabilization, the event is otherwise explained, or the participant is lost to follow-up (as defined in [Section 7.3](#)).

In general, follow-up information will include a description of the event in sufficient detail to allow for a complete medical assessment of the case and independent determination of possible causality. Any information relevant to the event, such as concomitant medications and illnesses, must be provided. In the case of a participant death, a summary of available autopsy findings must be submitted as soon as possible to Pfizer Safety.

Further information on -follow-up procedures is given in [Appendix 3](#).

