10.3.1. Definition of AE

AE Definition

• An AE is any untoward medical occurrence in a patient or clinical study participant, temporally associated with the use of study intervention, whether or not considered related to the study intervention.• Note: An AE can therefore be any unfavorable and unintended sign (including an abnormal laboratory finding), symptoms, or disease (new or exacerbated) temporally associated with the use of study intervention.

Events Meeting the AE Definition

• Any abnormal laboratory test results (hematology, clinical chemistry, or urinalysis) or other safety assessments (eg, ECG, radiological scans, vital sign measurements), including those that worsen from baseline, considered clinically significant in the medical and scientific judgment of the investigator. Any abnormal laboratory test results that meet any of the conditions below must be recorded as an AE:
• Is associated with accompanying symptoms;• Requires additional diagnostic testing or medical/surgical intervention;• Leads to a change in study dosing (outside of any protocol-specified dose adjustments) or discontinuation from the study, significant additional concomitant drug treatment, or other therapy.• Exacerbation of a chronic or intermittent preexisting condition, including either an increase in frequency and/or intensity of the condition.• New condition detected or diagnosed after study intervention administration, even though it may have been present before the start of the study.• Signs, symptoms, or the clinical sequelae of a suspected drug- interaction.• Signs, symptoms, or the clinical sequelae of a suspected overdose of either study intervention or a concomitant medication. Overdose per se will not be reported as an AE or SAE unless it is an intentional overdose taken with possible suicidal/self-harming intent. Such overdoses should be reported regardless of sequelae.

Events NOT Meeting the AE Definition

- Any clinically significant abnormal laboratory findings or other abnormal safety assessments that are associated with the underlying disease, unless judged by the investigator to be more severe than expected for the participant's condition.
- The disease/disorder being studied or expected progression, signs, or symptoms of the disease/disorder being studied, unless more severe than expected for the participant's condition.

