- The investigator is obligated to perform or arrange for the conduct of supplemental measurements and/or evaluations, as medically indicated or as requested by the sponsor, to elucidate the nature and/or causality of the AE or SAE as fully as possible. This may include additional laboratory tests or investigations, histopathological examinations, or consultation with other healthcare providers.
- If a participant dies during participation in the study or during a recognized follow-up period, the investigator will provide Pfizer Safety with a copy of any postmortem findings, including histopathology.

- New or updated information will be recorded in the originally submitted documents.
- The investigator will submit any updated SAE data to the sponsor within 24 hours of receipt of the information.

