#### **3.5.1. Adverse Events**

An adverse event (AE) is considered a Treatment-Emergent Adverse Event (TEAE) if the event started during the effective duration of treatment. All events that start on or after the first dosing day and time/start time, if collected, but before the last dose plus the lag time, will be flagged as TEAEs. The lag time is defined by the Pfizer Standard of 365 days post last dose of Ritlecitinib. The algorithm will not consider any events that started prior to the first dose date. If an AE starts on the same day as the first dose date, it will be considered treatment emergent unless the CRF data indicates otherwise via explicitly recording time for AE onset which was occurred before the first treatment dosing.

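### SAP 3.5.1 defines treatment-emergent AEs by onset alone, so the TEAE summary can miss an AE that is open at dosing and then worsens or becomes serious

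*Protocol*

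**What the plan says.** **Collection.** Under protocol 8.3.1 the active collection period "begins from the time the participant provides informed consent, which is obtained before the participant’s participation in the study". Section 8.3.1.2 puts on the CRF "All nonserious AEs and SAEs occurring in a participant during the active collection period, which begins after obtaining informed consent". On timing, section 8 states: "Participants will be screened within 28 days prior to administration of the study intervention". The Schedule of Activities then adds admission on Day -1 and the hours before the dose on Day 1.

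**Follow-up.** Protocol 8.3.3 states: "After the initial AE or SAE report, the investigator is required to proactively follow each participant at subsequent visits/contacts". The follow-up part of Appendix 3 adds: "New or updated information will be recorded in the originally submitted documents".

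**Classification.** Under SAP 3.5.1 an AE "is considered a Treatment-Emergent Adverse Event (TEAE) if the event started during the effective duration of treatment". The same section continues: "The algorithm will not consider any events that started prior to the first dose date". An event with onset on Day 1 counts as a TEAE unless the CRF explicitly records an onset time before the dose. The window stays open for 365 days after the dose.

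**Use.** TEAEs, laboratory tests and vital signs together form the secondary safety endpoint (protocol section 3, SAP 2.1). SAP 6.2.2.1 leaves the layout of AE reporting to the sponsor's reporting standards, which are not part of either document.

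**The concern.** A treatment-emergent definition should capture what changed after the drug was given. Two kinds of change qualify: an event that is new after dosing, and an event already present that becomes worse. SAP 3.5.1 covers only the first. A headache or nausea that starts mildly during the Day -1 stay and becomes severe after ritlecitinib has a pre-dose onset, and the algorithm passes over it if that onset is kept.

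The study has no control arm. Laboratory tests and vital signs have one routine scheduled post-dose assessment, on Day 3, and would not show a worse headache or nausea. The AE tables therefore carry most of the information on symptoms, and a misclassified participant is a visible share of an arm of about 8.

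**Working it through.** The plan states no AE rate, alpha or power for this point, and the sample size does not come from a formula. There is no figure of the plan's own to reproduce. The check is a reading of the rules against each other, then arithmetic for scale.

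**Step 1. Apply the SAP rule to possible records.** The cases are illustrations, not data.

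| Case | Onset on the record | TEAE under SAP 3.5.1? |
|---|---|---|
| Starts Day -5, resolves before dosing | Day -5 | No, correctly |
| Mild from Day -1, open at dosing, severe on Day 2, same record updated | Day -1 | No |
| Same event, worsening entered as a new record | Day 2 | Yes |
| Condition older than consent, worsens on Day 2, entered as an exacerbation | Day 2 | Yes |
| Starts on Day 1 before the dose, no time recorded | Day 1 | Yes, although it began before the dose |

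The second and third rows describe the same participant and differ only in how the CRF is completed.

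**Step 2. Look for an instruction that settles which row applies.** The AE definition in Appendix 3 includes "Exacerbation of a chronic or intermittent preexisting condition, including either an increase in frequency and/or intensity of the condition", which gives the fourth row its route to a post-dose onset. It does not say how to handle an AE first noted between consent and dosing. The instruction to put updates in the original documents leans towards keeping one record, but it says nothing about onset dates or severity changes. Protocol 10.1.7 refers to a separate CRF completion document, which is not available here. No text in the protocol or SAP requires a new record when an open AE worsens.

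**Step 3. Chance that it happens at all.** Inputs: 16 participants (protocol 4.1) and an assumed proportion *p* of participants with an AE that is open at dosing and worsens afterwards. Participants are taken as independent. Expected number = 16 × *p*; chance of at least one = 1 − (1 − *p*)^16.

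| Assumed *p* | Expected number of 16 | Chance of at least one |
|---|---|---|
| 0.5% | 0.08 | 1 − 0.995^16 = 7.7% |
| 1% | 0.16 | 1 − 0.99^16 = 14.9% |
| 2% | 0.32 | 1 − 0.98^16 = 27.6% |

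The low range reflects eligibility. Participants must be overtly healthy (inclusion criterion 2). Known active infection and febrile illness within 5 days of dosing are excluded (exclusion criteria 5 and 6). The criteria are checked again on Day -1.

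**Step 4. Effect of one such participant.** If that participant has no other TEAE, the arm's incidence falls by 1/8 = 12.5 percentage points with 8 participants, or 1/6 = 16.7 points with 6. The safety set is everyone dosed, so 8 is the natural denominator; 6 is the planned minimum of completers. If the participant has another TEAE, the incidence does not change and only the event count does.

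**The case against.** The strongest reply is that no undercount has been shown. If the CRF guidance or the sponsor's standards have worsening entered as a new record, the algorithm already counts it. That stands as a limit: the documents show that a deterioration can be missed, not that it will be. It does not close the gap, because documents outside the plan cannot be assumed to override a rule that the SAP states outright.

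A second reply is that nothing disappears. The event stays on the CRF, every SAE in the collection period goes to the sponsor's safety group within 24 hours (protocol 8.3.1.1), the SAP lists AEs in general among its safety data, and laboratory and vital-sign changes are summarised separately. This limits the harm, and with about 16 participants an event that turned serious would be noticed. It does not put the event into the TEAE summary.

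Some stronger readings are tempting, and the documents do not support them:

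- *Every event that begins before the dose is dropped.* A Day 1 event without a recorded onset time is counted.
- *The error can only make the drug look safer.* The same Day 1 rule can add events that truly began before the dose, and the 365-day window is generous. Only the missing worsening clause works in one direction.
- *Appendix 3 contradicts the SAP.* The contrast between a condition older than consent and an AE first recorded after consent appears only if updating the original record is read as fixing the onset date, which the text does not say.
- *A case is likely.* At an assumed 5% or 10% the formula gives 56.0% or 81.5%, but nothing in the documents supports rates that high in this population.

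**Conclusion.** The point holds as a gap in SAP 3.5.1. The collection period in the protocol is sound. The SAP's onset-only rule has no provision for worsening or seriousness after dosing, and no text secures the alternative route through a new record.

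The size is modest. The event most likely does not occur: a chance of about 8% to 28% under an assumed 0.5% to 2% of participants. If it does occur, it can move an arm's TEAE incidence by 12.5 points, or 16.7 points in an arm of 6, provided the participant has no other TEAE. The study is descriptive, with target occupancy as its primary endpoint and no hypothesis testing, so no formal conclusion depends on this. The case for acting is that a declared secondary endpoint has a classification gap that is cheap to close before analysis.

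**What to change.** Amend SAP 3.5.1 so that the definition reads: *A TEAE is an event that starts on or after dosing, or that was present before dosing and increases in severity or becomes serious after dosing.* Qualify the sentence that excludes events with a pre-dose start accordingly. The end of the window and the Day 1 timing rule can stay as they are.

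Add that each deterioration is counted once. If the CRF guidance enters worsening as a new record, flag only that new record; otherwise flag the original. Without this, one deterioration could be counted twice.

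Before finalising, confirm that the CRF dates a change in severity or seriousness. Appendix 3 asks for an intensity category for each AE but does not say whether a change is dated, and the algorithm needs to know that it came after the dose.

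No protocol amendment is needed: protocol section 9 allows the SAP to modify the plan and asks for an amendment only for major changes to the primary endpoint. No new assessments are involved. The cost is a short SAP edit, a check of the CRF guidance, and a TEAE count that may be slightly less favourable.

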8.3.2. Method of Detecting AEs and SAEs

The method of recording, evaluating, and assessing causality of AEs and SAEs and the procedures for completing and transmitting SAE reports are provided in [Appendix 3](#).

Care will be taken not to introduce bias when detecting AEs and/or SAEs. Open-ended and nonleading verbal questioning of the participant is the preferred method to inquire about AE occurrences.

8.3.3. Follow-up of AEs and SAEs

After the initial AE or SAE report, the investigator is required to proactively follow each participant at subsequent visits/contacts. For each event, the investigator must pursue and obtain adequate information until resolution, stabilization, the event is otherwise explained, or the participant is lost to follow-up (as defined in [Section 7.3](#)).

In general, follow-up information will include a description of the event in sufficient detail to allow for a complete medical assessment of the case and independent determination of possible causality. Any information relevant to the event, such as concomitant medications and illnesses, must be provided. In the case of a participant death, a summary of available autopsy findings must be submitted as soon as possible to Pfizer Safety.

Further information on -follow-up procedures is given in [Appendix 3](#).

8.3.4. Regulatory Reporting Requirements for SAEs

Prompt notification by the investigator to the sponsor of an SAE is essential so that legal obligations and ethical responsibilities toward the safety of participants and the safety of a study intervention under clinical investigation are met.

The sponsor has a legal responsibility to notify both the local regulatory authority and other regulatory agencies about the safety of a study intervention under clinical investigation. The sponsor will comply with country specific regulatory requirements relating to safety reporting to the regulatory authority, IRBs/ECs, and investigators.

Investigator safety reports must be prepared for SUSARs according to local regulatory requirements and sponsor policy and forwarded to investigators, as necessary.

An investigator who receives SUSARs or other specific safety information (eg, summary or listing of SAEs) from the sponsor will review and then file it along with the SRSD(s) for the study and will notify the IRB/EC, if appropriate according to local requirements.

8.3.5. Environmental Exposure, Exposure During Pregnancy or Breastfeeding, and Occupational Exposure

Environmental exposure occurs when a person not enrolled in the study as a participant receives unplanned direct contact with or exposure to the study intervention. Such exposure may or may not lead to the occurrence of an AE or SAE. Persons at risk for environmental exposure include healthcare providers, family members, and others who may be exposed. An environmental exposure may include exposure during pregnancy, exposure during breastfeeding, and occupational exposure.

Any such exposure to the study intervention under study is reportable to Pfizer Safety within 24 hours of investigator awareness.

8.3.5.1. Exposure During Pregnancy

An EDP occurs if:

- A female participant is found to be pregnant while receiving or after discontinuing study intervention.
- A male participant who is receiving or has discontinued study intervention exposes a female partner prior to or around the time of conception.

- A female is found to be pregnant while being exposed or having been exposed to study intervention due to environmental exposure. Below are examples of environmental EDP:
 - A female family member or healthcare provider reports that she is pregnant after having been exposed to the study intervention by ingestion.
 - A male family member or healthcare provider who has been exposed to the study intervention by ingestion then exposes his female partner prior to or around the time of conception.

The investigator must report EDP to Pfizer Safety within 24 hours of the investigator's awareness, irrespective of whether an SAE has occurred. The initial information submitted should include the anticipated date of delivery (see below for information related to termination of pregnancy).

- If EDP occurs in a participant or a participant's partner, the investigator must report this information to Pfizer Safety on the CT SAE Report Form and an EDP Supplemental Form, regardless of whether an SAE has occurred. Details of the pregnancy will be collected after the start of study intervention and until a minimum of 28 calendar days after last dose.
- If EDP occurs in the setting of environmental exposure, the investigator must report information to Pfizer Safety using the CT SAE Report Form and EDP Supplemental Form. Since the exposure information does not pertain to the participant enrolled in the study, the information is not recorded on a CRF; however, a copy of the completed CT SAE Report Form is maintained in the investigator site file.

Follow-up is conducted to obtain general information on the pregnancy and its outcome for all EDP reports with an unknown outcome. The investigator will follow the pregnancy until completion (or until pregnancy termination) and notify Pfizer Safety of the outcome as a follow-up to the initial EDP Supplemental Form. In the case of a live birth, the structural integrity of the neonate can be assessed at the time of birth. In the event of a termination, the reason(s) for termination should be specified and, if clinically possible, the structural integrity of the terminated fetus should be assessed by gross visual inspection (unless preprocedure test findings are conclusive for a congenital anomaly and the findings are reported).

Abnormal pregnancy outcomes are considered SAEs. If the outcome of the pregnancy meets the criteria for an SAE (ie, ectopic pregnancy, spontaneous abortion, intrauterine fetal demise, neonatal death, or congenital anomaly in a liveborn baby, a terminated fetus, an intrauterine fetal demise, or a neonatal death), the investigator should follow the procedures for reporting SAEs. Additional information about pregnancy outcomes that are reported to Pfizer Safety as SAEs follows:

- Spontaneous abortion including miscarriage and missed abortion;

- Neonatal deaths that occur within 1 month of birth should be reported, without regard to causality, as SAEs. In addition, infant deaths after 1 month should be reported as SAEs when the investigator assesses the infant death as related or possibly related to exposure to the study intervention.

Additional information regarding the EDP may be requested by the sponsor. Further follow-up of birth outcomes will be handled on a case-by-case basis (eg, follow-up on preterm infants to identify developmental delays). In the case of paternal exposure, the investigator will provide the participant with the Pregnant Partner Release of Information Form to deliver to his partner. The investigator must document in the source documents that the participant was given the Pregnant Partner Release of Information Form to provide to his partner.

